10.1. Background

Several clinical trials (including MIRCLE¹, MIRACLE-ICD², CONTAK-CD³, MUSTIC⁴, PATH-CHF⁵, COMPANION⁶, MADIT CRT⁷, and CARE-HF⁸) have demonstrated the benefit of cardiac resynchronization therapy (CRT) among patients with moderate to severe heart failure (HF) with a prolonged QRS duration and depressed Left Ventricular (LV) function.

Approximately 5.7 million people in the United States (US) are living with HF⁹. Heart Failure may be a chronic condition which causes the heart to not pump oxygenated blood efficiently through the body due to stiffening of the heart muscle. Heart Failure may affect one or both sides of the heart. It is most often caused by coronary artery disease (CAD) or uncontrolled hypertension (HTN). Patients who suffer from HF experience a variety of different symptoms including most often fatigue, cough, shortness of breath, swollen feet (edema) and weight gain.

Heart Failure is treated with medications and sometimes cardiac devices (i.e. pacemaker or defibrillator with CRT). Medications work to relieve symptoms and reverse the effects of HF. Cardiac Resynchronization Therapy devices treat HF by synchronizing the left and right ventricles of the heart which improves the heart's ability to pump oxygenated blood to the body.^{10 11 12 13 14 15 16 17 18 19 20 21}

Cardiac Resynchronization Therapy devices are primarily made up of 4 main components; the can or battery, a Right Atrial (RA) lead, a Right Ventricular (RV) lead, and a Left Ventricular (LV) lead.

The LV lead specifically is important at maintaining ventricular synchrony. In 2014, Medtronic released the Attain® Performa™ family of LV leads (models 4298, 4398 and 4598). The three different shapes of these leads (double canted, straight, and S-shaped) were designed to enable the lead to be passively fixed within different anatomies of coronary vessels. In addition, the 4 strategically placed electrodes on the lead were designed to offer 16 different electrical vector programming configurations.

Medtronic also released the Attain Stability bipolar LV lead (Model 20066/4796) (CE Mark approved in September 30, 2013) in Europe. This lead has a side helix which enables it to be actively fixated to the vessel wall. The active fixation is an advantageous component in vessels that are wide or have short take-offs. The next generation of LV lead is known as the Attain Stability™ Quad MRI SureScan LV lead (Model 4798). This is a quadripolar lead similar to its Attain Performa predecessor leads and has a side helix for active fixation like the Attain Stability bipolar lead.

10.2. Purpose

The Attain Stability Quad Clinical Study is a prospective, non-randomized, multi-site, global, Investigational Device Exemption (IDE), interventional clinical study. The purpose of this clinical study is to evaluate the safety and efficacy of the Attain Stability™ Quad MRI SureScan LV Lead (Model 4798). This study will not be considered investigational in geographies with CE Mark of the Attain Stability™ Quad MRI SureScan LV lead (Model 4798). However, data collected from all study subjects will be represented in the final clinical report and the PMA Supplement (PMA-S) to the Attain Ability Model 4196 Original PMA (P080006, approved April 7, 2009). Subjects successfully implanted with the Attain Stability Quad MRI SureScan LV Lead (Model 4798) will be followed at implant, three months, six months and every six months thereafter until FDA approval is obtained or until study closure, whichever comes first.

11. Objectives and Endpoints

11.1. Objectives

11.1.1. Primary Objective(s)

Primary Safety Objective: Lead complication-free rate at 6 months

The Attain Stability Quad MRI SureScan LV Lead (Model 4798) will be considered safe if the probability of subjects free of Model 4798 lead-related complications at 6 months post-implant is greater than 87% (i.e., the lower bound of a one-sided 97.5% confidence interval must be greater than 87%).

Primary Efficacy Objectives: Lead pacing capture thresholds at 6 months

To demonstrate the effectiveness of the Attain Stability Quad MRI SureScan LV Lead (Model 4798), the study will evaluate the likelihood that there are at least two programmable vectors for each patient post implant. The effectiveness of this lead will be evaluated based on two primary efficacy objectives. More specifically, both primary efficacy objectives must be met simultaneously.

Primary Efficacy Objective #1

The Attain Stability Quad MRI SureScan LV Lead (Model 4798) will meet this objective if the proportion of subjects with at least one LV lead pacing vector having a pacing capture threshold less than or equal to 2.5 V at 0.5 ms pulse width at 6 months post-implant is greater than 80% (i.e., the lower bound of a one-sided 97.5% confidence interval must be greater than 80%).

Primary Efficacy Objective #2

The Attain Stability Quad MRI SureScan LV Lead (Model 4798) will meet this objective if the proportion of subjects with at least one additional (or second) LV lead pacing vector having a pacing capture threshold less than or equal to 4.0 V at 0.5 ms pulse width at 6 months post-implant is greater than 80% (i.e., the lower bound of a one-sided 97.5% confidence interval must be greater than 80%).

11.1.2. Secondary Objective(s)

The secondary objectives are descriptive in nature and are intended to provide additional information about the Attain Stability Quad MRI SureScan LV Lead (Model 4798). There will be no established performance requirements for these secondary objectives.

- To summarize implant procedure related information: success rate, implant related times
- To estimate 6-month reliability: post implant lead failure modes (i.e. complication rate)
- To estimate electrical measurement values (Pacing Capture Thresholds (PCTs) and Lead Impedance) at 6 months post-implant

11.2. Endpoints**11.2.1 Primary Endpoints****Primary Safety Endpoint**

The study primary safety endpoint is Attain Stability Quad MRI SureScan LV Lead (Model 4798) related complications through 6 months post implant. All reported system and procedure-related AEs will be reviewed by an event review committee for LV lead relatedness and severity (complication vs observation, refer to 17.1.2 for definitions).

Primary Efficacy Endpoint #1

The Model 4798 LV lead has sixteen (16) programmable pacing vectors. The endpoint for the primary efficacy objective is whether or not there is at least one Model 4798 LV lead pacing vector with pacing capture voltage thresholds less than or equal to 2.5V. This endpoint will be measured at the 6-month post implant follow-up visit.

Primary Efficacy Endpoint #2

The co-primary efficacy endpoint is whether or not a second Model 4798 lead configuration has a pacing capture threshold less than or equal to 4V, excluding the pacing vector that is already counted to the primary efficacy endpoint #1. This endpoint will be measured at 6-month post implant follow-up visit.

11.2.2 Secondary Endpoints**To summarize implant procedure related information**

Implant procedure related endpoints will include implant success rate and procedure durations.

To estimate 6-month reliability

The Model 4798 LV lead 6-month reliability endpoint is Model 4798 lead related complications.

To estimate electrical measurement values (Pacing Capture Thresholds (PCTs) and Lead Impedance) at 6 months post-implant

The electrical measurements are pacing capture thresholds and impedance values for the four extended bipolar (CRT-D) vectors (i.e. LV1 to RVCoil, LV2 to RV Coil, LV3 to RV Coil, LV4 to RV Coil) or the unipolar (CRT-P) vectors (i.e. LV1 to Can, LV2 to Can, LV3 to Can, LV4 to Can) (refer to 15.8.2.3 for the testing procedure requirements).

[figure not shown]
12. Study Design

The Attain Stability Quad Clinical Study is a prospective, non-randomized, multi-site, global, Investigational Device Exemption (IDE), interventional clinical study. The purpose of this clinical study is to evaluate the safety and efficacy of the Attain Stability Quad MRI SureScan LV Lead (Model 4798) in patients indicated for a de novo LV lead implant. This will be assessed through a primary safety and primary efficacy endpoints.

All subjects included in the study will be implanted with a Medtronic market released de novo CRT-P or CRT-D device and an Attain Stability Quad MRI SureScan LV Lead (Model 4798). Compatible market released Medtronic RA and Medtronic RV leads will be required. For subjects enrolled who are receiving an upgrade to a CRT system, existing non-Medtronic RV and/or existing non-Medtronic RA leads that are not recalled, market withdrawn, and/or have a medical alert may be used.

Up to 471 subjects will be enrolled into the study and up to 471 Attain Stability Quad MRI SureScan LV Lead (Model 4798) implanted, to ensure a minimum effective sample size of 400 Model 4798 leads implanted with 6 months post implant follow up visits (assuming 15% attrition). For the secondary endpoint of individual lead failure modes, Bayesian methods utilizing data from up to 37 historical patients will be used. All other objectives will be analyzed using only patients enrolled in this study. After a successful implant, threshold testing will occur to show one LV vector with pacing capture threshold (PCT) ≤ 2.5 [contact] and with sufficient safety margin was programmed. Subjects will then be followed at implant, three months, six months and every six months thereafter until FDA approval is obtained or until study closure, whichever comes first.

See Figure 1 and Section 15 for further detail on study procedures and data collection as well as time-points for data collection.

Figure 1: Study Visits

The study is expected to be conducted at up to 56 sites worldwide. Participating geographies are expected to include, but are not limited to: the United States, Canada, EMEA, Malaysia, and Hong Kong. To ensure a widespread distribution of data and to minimize site bias in the study results, the maximum number of subjects allowed at a single site is 50 subjects.

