
Study Design
	
The Attain Stability Quad Clinical Study is a prospective, non-randomized, multi-site, global, Investigational Device Exemption (IDE) interventional clinical study. The purpose of this clinical study is to evaluate the safety and efficacy of the Attain Stability Quad MRI SureScan LV lead (Model 4798) in patients indicated for a de novo LV lead implant. This will be assessed through primary safety and primary efficacy endpoints.
 
All subjects included in the study will be implanted with a Medtronic market released de novo CRT-P or CRT-D device and an Attain Stability Quad MRI SureScan LV Lead (Model 4798). Compatible market released Medtronic RA and Medtronic RV leads will be required. For subjects enrolled who are receiving an upgrade to a CRT system, existing non-Medtronic RV and/or existing non-Medtronic RA leads that are not recalled, market withdrawn, and/or have a medical alert may be used.
 
Up to 471 subjects will be enrolled into the study and up to 471 Attain Stability Quad MRI SureScan LV Leads (Model 4798) implanted, to ensure a minimum effective sample size of 400 Model 4798 leads implanted with 6 months post implant follow up visits (assuming 15% attrition). For the secondary endpoint of individual lead failure modes, Bayesian methods utilizing data from up to 37 historical patients will be used. All other objectives will be analyzed using only patients enrolled in this study.
 
After a successful implant, threshold testing will occur per protocol requirement. Subjects will then be followed at implant, three months, six months and every six months thereafter until FDA approval is obtained or until study closure, whichever comes first.
 
The study duration is expected to be approximately 19 months. This represents 13 months for subject enrollment and 6 months for subject follow-up for the last subject enrolled. Subjects are anticipated to be in the study for on average 12 months. The first enrollment is projected to occur in May 2017.

Sample Size
	
Up to 471 subjects will be enrolled into the study, to ensure a minimum effective sample size of 400 Model 4798 leads implanted with 6 months post implant follow up visits (assuming 15% attrition) at up to 56 sites worldwide.

Inclusion/Exclusion Criteria
	
Inclusion Criteria:
 
 • Patient meets CRT implant criteria as determined

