15.8.1. Final System Configuration

For information on the requirements for the implanted system refer to Section 13. The system is successfully implanted when the Medtronic CRT device is successfully connected to the RA, RV and the LV lead (except if a medical condition such as chronic atrial fibrillation excludes the need for an RA lead). The configuration of the successfully implanted system components will be collected. This will include the serial number of each implanted component (CRT-D or CRT-P device, and leads), and the location of lead placement.

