In an event that one Attain Stability Quad MRI SureScan LV Lead (Model 4798) is determined to be not suitable for a patient after the initial lead insertion; the implanting physician must assess the onset of any potential AEs. A second Attain Stability Quad MRI SureScan LV Lead (Model 4798) may only be introduced upon confirmation that no system-related AEs resulted from the first Attain Stability Quad MRI SureScan LV Lead (Model 4798) implant attempt. Any LV lead related AE observed during the initial LV lead attempt prohibits an attempt of a second Attain Stability Quad MRI SureScan LV Lead (Model 4798).

If the subject does not have a successful Attain Stability Quad MRI SureScan LV Lead (Model 4798) implant at the conclusion of the initial implant procedure, the subject should be followed until procedure or system related AEs are resolved or are unresolved with no further actions planned, whichever occurs later.

If an attempt to implant the Attain Stability Quad MRI SureScan LV Lead (Model 4798) does not occur, or if the Model 4798 LV lead cannot be implanted, the reasons why the lead was not attempted or attempted but not implanted must be documented on the Implant and Study Exit CRF. See additional definitions below.

No Attain Stability Quad MRI SureScan LV Lead (Model 4798) Attempted (lead not inserted into the body)

An Attain Stability Quad MRI SureScan LV Lead (Model 4798) attempt is defined as any time a Model 4798 lead is introduced into the body. Subjects that do not have an Attain Stability Quad MRI SureScan LV Lead (Model 4798) implant attempted will be exited from the study following their implant procedure

unless another Attain Stability Quad MRI SureScan LV Lead (Model 4798) attempt is scheduled. Adverse events, device deficiencies and deviations must be documented before the subject is exited.

Attain Stability Quad MRI SureScan LV Lead (Model 4798) Attempted but Not Implanted

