An Attain Stability Quad MRI SureScan LV Lead (Model 4798) that is inserted into the body that is not successfully placed will be considered an unsuccessful Attain Stability Quad MRI SureScan LV Lead (Model 4798) attempt. Note: An unsuccessful implant itself is not considered an AE. Adverse Events occurring during an unsuccessful implant (e.g. dissection, perforation) will be recorded and classified. Subjects with an unsuccessful Attain Stability Quad MRI SureScan LV Lead (Model 4798) attempt will be followed until procedure or system related AEs have been resolved or are deemed unresolvable with no further action planned.

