15.8.2.3. CRT System Testing and Programming During Implant

Prior to connecting the leads to the CRT can, initial electrical measurements will be taken using the Analyzer (Model 2290 or market released equivalent) to confirm adequate pacing thresholds (PCTs) prior to closing the pocket per the site's standard testing method. These PCTs will be collected on the same vector, at two timepoints once the lead is fixated and prior to connecting the leads to the can using the Analyzer. The timepoints are as follows;

- 1.) Prior to slitting the cannulation catheter – Collect the first PCT using the Analyzer after the lead is fixated and the guidewire/stylet has been pulled back proximal to the helix and electrodes.
- 2.) Post slitting the cannulation catheter – Collect the second PCT using the Analyzer after the lead is fixated and following slitting of the cannulation catheter.

These PCT measurements will be collected on the CRF. This data will only be collected if an Attain Stability Quad MRI SureScan LV Lead (Model 4798) is successfully placed.

Pacing voltage thresholds are measured to determine whether the underlying myocardium will respond effectively to pacing and to evaluate lead stability in the cardiac vein. It is required to perform LV pacing threshold measurements during implant using the pacing threshold test at a 0.5ms pulse width. It is recommended to begin at 2.5 Volts and decrease amplitude after at least 3 pulses until capture is lost. If there is no capture at 2.5 V; stop the test and repeat at a higher voltage using the 0.5ms pulse width. The lowest amplitude where capture consistently occurs is the pacing threshold value. Collect data using the Analyzer (Model 2290 or market released equivalent).

It is recommended that physicians locate a final LV pacing site that can be captured using less than or equal to 2.5 V at 0.5ms, R-wave sensing of at least 4.0 mV, and does not cause diaphragmatic stimulation at 10V at 0.5ms. For additional details regarding the left ventricular leads and implant tools, refer to the respective technical manuals provided with each product.

Individual patient venous anatomies as well as pathologies present in the left ventricular myocardium are factors that will influence LV lead placement. Therefore, the best cardiac vein lead electrode location to stimulate the LV may vary for each patient.

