The primary efficacy endpoint will be analyzed using the Exact binomial method. In order to preserve the overall study power, a type II error less than 10% was used for the sample size calculation. A sample size of 145 subjects achieves 91% power to detect a difference of 0.1 using a one-sided binomial test at a target significance level of 0.025. These results assume that the population proportion under the null hypothesis is 80%, with an expected proportion of 90%.

Determination of Patients / Data for Analysis

All subjects enrolled into this study satisfying the following conditions will be included in this analysis:

- Successfully implanted with a Medtronic Quad CRT-P or CRT-D device and Attain Stability Quad MRI SureScan LV Lead (Model 4798)
- Completed 6-month follow-up visit
- Initially implanted Attain Stability Quad MRI SureScan LV Lead (Model 4798) is active at the 6-month follow-up visit
- At least one available and valid pacing threshold at the 6-month follow-up visit

19.1.3. Primary Efficacy Objective # 2

Objective

The Attain Stability Quad lead will meet the second primary efficacy objective if the proportion of subjects with at least one additional (or second) LV lead pacing vector having a pacing capture threshold less than or equal to 4.0 V at 0.5ms pulse width at 6 months post-implant is greater than 80% (i.e., the one-sided 97.5% lower confidence bound must be greater than 80%).

Hypothesis

$$H_0: P_{2_{6\text{-month}}} \leq 80\%$$

$$H_A: P_{2_{6\text{-month}}} > 80\%$$

where $P_{2_{6\text{-month}}}$ is the proportion of subjects with at least one additional LV lead pacing vector with pacing voltage thresholds $\leq 4.0V$ at 0.5ms at 6 months post-implant follow-up visit.

Endpoint Justification

The Attain Stability Quad MRI SureScan LV Lead (Model 4798) has 16 LV programmable pacing vectors . Subjects may have the pacing configuration programmed or reprogrammed at each clinic visit. A pacing threshold of 4.0 V will allow an adequate safety margin for programming LV pacing output. The maximum pacing amplitude of the CRT-P or CRT-D devices capable of programming pacing output to any LV lead pacing vector is 8.0V. In actual clinical practice, a less than 3V safety margin is used for the programmed LV lead pacing output in 99% of the patients.

Statistical Analysis Methods

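### Leads given up at implant on a threshold equal to the efficacy #1 cut-off drop out of the efficacy sets and the worst-case analysis, and the 2.5 V wording in section 12 should be reconciled with the synopsis and section 15.8.2.3

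*Protocol*

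**What the plan says.** Three passages of the version 2.0 text touch on 2.5 V at or just after implant.

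- **Section 12** says that after a successful implant "threshold testing will occur to show one LV vector with pacing capture threshold (PCT) ≤ 2.5", with a sufficient safety margin programmed. Part of the sentence, including the unit, is masked in the copy at hand; I read it as volts.
- **The synopsis (section 9, Study Design)** has at the same place: "After a successful implant, threshold testing will occur per protocol requirement". The version 1.0 synopsis carried the 2.5 wording, so one copy was revised and the other was not.
- **Section 15.8.2.3** says: "It is recommended that physicians locate a final LV pacing site that can be captured using less than or equal to 2.5 V" (pulse width 0.5 ms).

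The other provisions that matter are these.

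- Primary efficacy endpoint #1 (section 11.2.1) is whether there is "at least one Model 4798 LV lead pacing vector with pacing capture voltage thresholds less than or equal to 2.5V" at 6 months.
- Implant success (section 15.8.1) is defined by connection: "The system is successfully implanted when the Medtronic CRT device is successfully connected to the RA, RV and the LV lead". No threshold enters.
- Section 15.8.2.2 lets a lead be given up when it "is determined to be not suitable for a patient after the initial lead insertion", without a criterion. It adds: "An unsuccessful implant itself is not considered an AE".
- Both efficacy sets (sections 19.1.2 and 19.1.3) require that the subject was "Successfully implanted with a Medtronic Quad CRT-P or CRT-D device and Attain Stability Quad MRI SureScan LV Lead (Model 4798").
- The worst-case analysis in section 19.3.2 is likewise confined to subjects with a successful implant.

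**The concern.** The value recommended for the final pacing site is the same number that later defines efficacy success. An operator who reads a high threshold on the analyzer and gives up the Model 4798 lead during the procedure has selected on a close precursor of the endpoint. The subject is then in the attempted-but-not-implanted category, which is not in itself an adverse event. Unless another Model 4798 lead is placed, the subject is followed only briefly and exited (section 15.16.2).

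The efficacy proportion is computed among the leads that remain. It rises if the abandoned leads would have failed more often than those kept. The one analysis in the protocol meant to test excluded subjects cannot show this, because it starts from the same condition of successful implant.

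The differing 2.5 V wording in sections 9, 12 and 15.8.2.3 is a separate matter. It leaves a reader unsure what status the figure has.

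**Working it through.** **The plan's own figure.** For efficacy #1 the inputs in section 19.1.2 are a null of 80%, an expected 90%, one-sided 0.025, the exact binomial and N = 145. The smallest passing count is 126/145 (exact lower limit 80.3%). Then P(X ≥ 126 | 0.80) = 0.0204 and P(X ≥ 126 | 0.90) = 0.913. The stated 91% power reproduces. Nothing is wrong with the sample size.

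**Who is lost, and where.** The path depends on when the lead is given up.

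| Moment | Governing section | Status | In efficacy set? | In 19.3.2 worst case? |
|---|---|---|---|---|
| During the procedure, on the analyzer reading | 15.8.2.2, 15.8.2.3 | Attempted, not implanted | No | No |
| After connection, on device testing | 15.8.2.5, 15.14 | Successful implant, then system modification | Not if the initial lead is inactive at 6 months | Yes, as failure |

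Only the first row escapes both analyses.

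**Illustration of size.** Let p be the true success rate among all attempts, f the share of attempts abandoned for threshold, and s the share of those abandoned that would have succeeded at 6 months. The success rate in the analysed set is

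q = (p − f·s)/(1 − f),

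which exceeds p whenever s < p. Take p = 0.80 (the null) and 400 attempts (the overall 6-month target in Table 18), ignoring other attrition. With no abandonment the exact test passes at 336/400 (lower limit 80.03%; 335 gives 79.76%), and P(pass) = 2.4%.

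| f (assumed) | n analysed | Passing count | q if all would fail (s = 0) | P(pass) | q if half would fail (s = 0.5) | P(pass) |
|---|---|---|---|---|---|---|
| 2% | 392 | 330 | 0.80/0.98 = 0.8163 | 10.6% | 0.79/0.98 = 0.8061 | 4.0% |
| 5% | 380 | 320 | 0.80/0.95 = 0.8421 | 53.4% | 0.775/0.95 = 0.8158 | 10.3% |
| 8% | 368 | 310 | 0.80/0.92 = 0.8696 | 94.5% | 0.76/0.92 = 0.8261 | 22.7% |

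Both f and s are assumptions; the protocol gives neither. The case s = 0 is an upper extreme. Section 15.8.2.3 collects the analyzer threshold on one vector, while the endpoint needs only one of 16 vectors at 6 months. A high reading at implant is therefore an imperfect predictor of failure.

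**The case against.** A reader might infer that section 12 sets a standard for accepting the lead, so that sites following it would withdraw leads above 2.5 V while sites following the synopsis would leave them in. The documents do not support that. The section 12 sentence concerns testing after a successful implant, and success is defined by connection. A lead removed after that point is a system modification under section 15.14, and the subject is counted as a failure in the worst case of section 19.3.2. Nothing in section 12 tells a site to withdraw a lead, and the synopsis does not tell a site to keep one. The selection runs through section 15.8.2.3 and the operator's judgement, and it would persist however the wording is aligned.

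Other points on that side also stand.

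- The lead may be repositioned, or a second Model 4798 lead tried if no system-related AE resulted (section 15.8.2.2), so a high reading need not end in loss.
- Abandonment is not hidden. Implant success per attempt is reported with an exact 95% interval (section 19.2.1), and the safety cohort includes every attempt.
- Efficacy is openly conditional on an implanted, active lead. Counting abandoned leads as failures answers a different question, which is why it belongs in a supplementary result.
- The sponsor's simulated 89% success excludes the most distal electrode, so its complement of 11% should not be read as the share of leads at risk of abandonment.

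These points limit the concern without removing it. The implant success rate is never carried into the efficacy proportion, and section 19.2.1 does not separate threshold from other reasons for abandonment.

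**Conclusion.** Two things hold. First, the 2.5 V wording in section 12 differs from the version 2.0 synopsis and from section 15.8.2.3, and the three should be reconciled. Second, subjects whose lead is given up during the procedure on analyzer threshold are selected on the efficacy #1 cut-off, and they fall outside both efficacy sets and the worst-case analysis.

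The size, and the direction by site, are unknown. The illustrated chance of a false pass (2.4% with no abandonment, 4-11% at 2% of attempts, 10-53% at 5%) rests on an assumed abandonment rate, an assumed failure share, a true rate exactly at the null and 400 attempts. It is not an estimate for this trial. It would go too far to say that the efficacy result cannot be read as lead performance; it can be read as performance among implanted leads, and what is missing is a check on how far that condition matters.

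**What to change.** Reconcile sections 9, 12 and 15.8.2.3 so that the status of the 2.5 V figure is stated once. Which status is right is for the sponsor and the clinical team.

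Add to section 19.3.2 a supplementary result for both efficacy objectives. It would include subjects whose Model 4798 lead was attempted but not implanted because of capture threshold, counted as failures, with their number shown by geography. For objective #2, whose cut-off is 4.0 V, this is a deliberately pessimistic bound. Identify the subjects from the reason that section 15.8.2.2 already requires on the Implant and Study Exit CRF. The analyzer readings cannot serve, because section 15.8.2.3 collects them only when the lead is successfully placed.

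The primary analysis, sample size and visits are unchanged. The cost is a wording correction and one extra table; the downside is a supplementary proportion slightly less favourable than the primary one.
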